($P<0.001$), and HbA1c improved by 0.70 (1.13) vs. 0.39 (1.51) in group lifestyle vs. RD-MNT ($P=0.38$), respectively. There was no difference in blood pressure or lipid levels between interventions; however, 14% in group lifestyle stopped a blood pressure medication vs. none in RD-MNT ($P=0.046$). Weight loss remained significantly greater in group lifestyle compared to RD-MNT at one year. Group lifestyle program cost was \$578 per patient. Including changes in personnel and medication costs, the group lifestyle program cost \$146 per patient more than RD-MNT.

c. Rationale behind the proposed research, and potential benefits to participants and/or society

Although it is tempting to directly translate successful research methods into clinical care without a demonstration that the methodology developed and implemented in a clinical trial is effective in a clinical setting, attempts to directly translate such programs can be both ineffective and expensive. The challenge of demonstration translational studies is to ensure that the interventions are practical and effective, and in turn easily applied to clinical practice. If the Look AHEAD lifestyle program proves to be effective in the proposed translation study, subsequent steps will include determining how to expand the program to other clinical settings more broadly. The goal of this study is to translate the lifestyle program proven in the two national clinical studies and the IDOLc pilot study to result in weight loss of 5-10%, increased activity to 175 minutes/week, decreased hemoglobin A1c (HbA1c), blood pressure, lipid levels, and reduced medications used to treat these conditions into usual care at MGH Community Health Centers and practices in communities affected by diabetes and obesity, and to determine the reach, cost-effectiveness, and sustainability of the program. Two intervention modalities, in person group or telephone conference call group, will be tested against referral to dietitians for individual medical nutrition therapy (MNT), the current standard of care.

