Aim 3: To estimate the incremental cost per percentage point decrease in body weight of the implementation strategies assessed in this study compared to usual care. The focus of our analysis will be identifying short-term costs and health effects that are relevant to accountable care organizations and insurers with the goal of informing the design of payment contracts that ensure the adoption of effective and efficient diabetes care, with a particular focus on the tradeoffs between costs and effectiveness of telephone compared to in-person format.

III. SUBJECT SELECTION

a) Inclusion/exclusion criteria

Eligibility criteria for participation include:

- Diagnosis of type 2 diabetes
- Age 18 years or older
- Overweight or obese ($BMI > 25 \text{ kg/m}^2$) unless of Asian descent then BMI criterion is lowered to $BMI > 23 \text{ kg/m}^2$
- HbA1c level $6.5 < 11.5\%$
- Systolic blood pressure (SBP) $< 160 \text{ mmHg}$, diastolic blood pressure (DBP) $< 100 \text{ mmHg}$
- Willing to lose 5-7% of body weight
- Willing to increase activity to at least 175 minutes/week
- Willing to commit to random assignment to either attend and participate in the lifestyle change program in person or on the telephone or be referred to Nutrition Services for medical nutrition therapy
- Stable health, with no severe comorbidities that might interfere with their ability to participate in a group intervention that includes increasing activity or decreasing calories, such as severe psychiatric illness or significant heart disease
- Ability to understand and communicate effectively in English or Spanish
- Willing to self-monitor blood glucose
- Willing to keep a food, exercise, and blood glucose diary

- Have a primary care physician at MGH Chelsea, Charlestown, Revere Health Centers, or any Partners affiliated practices or be willing to attend sessions, in-person or by phone, and have medications adjusted by a provider based at one of those health centers or the MGH Diabetes Center with communication to the referring primary care provider

Exclusion criteria include:

- Weight greater than 350 pounds
- Pregnant or planning pregnancy in the next year
- Currently seeing a dietitian (regular scheduled follow up appointments) or participating in a weight loss program and unwilling to stop
- Weight change of more than 3% body weight in the previous 1 month.
- Currently enrolled in another diabetes study
- Lack of availability of telephone

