Primary data will be collected for the three study arms. Each study arm has several cost components. These include the **cost of personnel time**, defined by the differential use of time physicians, nurse practitioners, dietitians, and medical assistants will spend on the project, as well as the **cost of services provided**, including medication utilization, health care utilization not included in clinician time/reimbursement, program materials, and office space. We will also track patient time use, as well as telephone minute, transportation, and parking costs to understand the relative financial burden each strategy places on participants.

Cost of personnel time. Provider time use will be monitored using sessions delivered and self-report augmented by limited direct observation. Total time devoted to training, outreach, session delivery, and patient contact will be estimated by multiplying the total number of times a task was performed by the average time devoted to the task. Dietitian referral time will be counted by review of completed visit notes which document time. We will assess the total cost of time, including time spent on record review and between-visit contact, if any, based on the value of each person's time in hourly wages (salary plus benefits). Direct observation will determine how

much time is spent on coordination tasks. Patient time use will be measured using survey assessments and valued using labor statistics data adjusted by age and residence.

Cost of services provided. Cost of services will be estimated using existing data sources, including inpatient and outpatient billing and reimbursement data, patient self-reports (prescriptions filled), and study data on sessions attended. We will compare the total costs in each arm over the study period.

Personnel time, program materials, office space, patient telephone minutes, and parking costs will be derived from study records.

Patient travel costs and telephone minute costs will be collected at RV2, 3, and 4 [see “18. Patient Travel and Phone Use”].

Dose, type, fill rate, and co-pays for medications and use of health care services will be collected by telephone every 6 months until year 3 (RV5) using pre-populated forms mailed to the participant 1 week before the scheduled call to facilitate accurate medication collection.

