This aim is largely qualitative. For quantitative outcomes we will compare if appropriate but the study is not powered to perform statistical analysis on RE-AIM measures.

Aim 3:

We will estimate the cost of each treatment model, and compare the incremental cost-effectiveness as $((\text{total cost[treatment model}_i] - \text{total cost[treatment model}_j]) / (\text{average \% weight loss[treatment model}_i] - \text{average \% weight loss[treatment model}_j))$. A formal cost-utility analysis (cost per QALY saved) is beyond the scope of this project, but we will collect data that may be used for a future effort if the intervention is effective.

The study was not designed to be powered for detecting differences in cost outcomes, but we will use standard modeling methods (e.g. Monte Carlo analyses) to account for uncertainty in cost outcomes when calculating incremental cost-effectiveness.

VII. RISKS AND DISCOMFORTS

The risks to the participants will be minor, and be limited to 1) blood drawing, 2) discomfort answering questions 3) risks of intervention 4) risks of exercise 5) loss of confidentiality. We will address these sequentially.

Blood drawing will be minimal. Five blood draws (total 6 cc) will be taken, one at baseline and one each at 6, 12, 24, and 36 months. Results of these blood draws will also be used for usual care. Participants may experience a small amount of pain. Occasionally a bruise may be produced. There is also a small risk of infection, lightheadedness, and/or fainting. Fasting overnight will be required, however a snack will be offered after the blood draw.

Discomfort answering questions. Some participants may feel uncomfortable answering questions about their diabetes, health, nutrition and daily activity. Participants will be told that that they may skip over the questions in the questionnaires that they do not want to answer.

Risks of the intervention: Changing diet and exercise and losing weight may cause hypoglycemia or hypotension. Participants in the group lifestyle intervention will be asked to submit weekly food, activity and blood glucose records which will be reviewed by the study provider who will make any needed adjustments in diabetes medications to prevent hypoglycemia. With every 10 lbs of weight loss, it will be recommended to patients to have their blood pressure monitored according to the protocol outlined below. Participants receiving usual care will continue to be managed by their primary care physician.

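### As written, the Aim 3 ratio divides a difference in total costs by a difference in per-person mean weight loss, so it depends on how many participants contribute costs

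*Combined protocol and SAP*

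**What the plan says.** Section II states Aim 3 as: "To estimate the incremental cost per percentage point decrease in body weight of the implementation strategies assessed in this study compared to usual care". Section VI.d (Aim 3) turns this into a formula: "We will estimate the cost of each treatment model, and compare the incremental cost-effectiveness as" a ratio of two differences. The numerator is the total cost of model i minus that of model j. The denominator is the average percent weight loss of model i minus that of model j. The same section says the study is not powered for cost outcomes and plans Monte Carlo methods for cost uncertainty.

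Section V (AIM 3, cost of services provided) says: "We will compare the total costs in each arm over the study period". Under cost of personnel time, the total time spent on each activity "will be estimated by multiplying the total number of times a task was performed by the average time devoted to the task". That builds personnel cost from aggregate counts.

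A per-patient cost appears only in the pilot results in Section I: "Group lifestyle program cost was \$578 per patient", and "Including changes in personnel and medication costs, the group lifestyle program cost" 146 dollars per patient more than dietitian referral.

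The formula names no time point. Weight is measured at 6, 12, 24 and 36 months. In Section V, medication and service use are collected to year 3, travel and telephone costs at RV2 to RV4, and other diabetes care and costs to 24 months. No rule covers participants with incomplete cost data. Section VI.b lists cost as a secondary outcome, but the outcomes named for the mixed model in Section VI.c do not include it.

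**The concern.** One expression uses a total above the line and an average below it. If the total is a sum over everyone in an arm, the ratio grows with the number enrolled and is not a property of the intervention. It could not be set beside the pilot's per-patient costs or carried to a program of another size. The aim is meant to inform how accountable care organizations and insurers design payment contracts, so the unit matters to the intended reader.

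The more serious risk arises when the arms do not contribute equal numbers of people, or equal follow-up, to the cost total. The difference in totals then mixes the cost difference per person with the difference in head count, and the head-count part is multiplied by the whole cost of care per person.

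**Working it through.** **Inputs.** Pilot incremental cost 146 dollars per patient and pilot program cost 578 dollars per patient (Section I). Pilot difference in mean weight loss 4.1 percentage points, planned arm size 70, drop-out 10% (Section VI.d). Allocation 1:1:1 within site, stratified by sex (Section VI.c). The plan states no numerical ratio for Aim 3 and gives no MNT cost per participant, so the MNT costs below are assumptions.

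**Arm size, the multiplier in question.** A two-sample t calculation with difference 3.5, SD 5.5, two-sided alpha 0.05/3 and 80% power needs 53.2 per arm. The plan's 54 gives 80.7% power. Inflating, 54 × 1.18 / 0.9 = 70.8, where 1.18 = 1 + 9 × 0.02 for groups of 10; with the plan's rounded factor, 54 × 1.2 / 0.9 = 72. The stated 70 is reproduced closely enough.

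**Equal arms.** Let c be the MNT cost per participant and c + 146 the lifestyle cost.

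- Per-participant ratio: 146 / 4.1 = 35.6 dollars per point, at any arm size.
- Literal ratio at 70 per arm: 70 × 146 / 4.1 = 10,220 / 4.1 = 2,493 dollars per point.
- Literal ratio at 63 per arm (10% fewer in both): 63 × 146 / 4.1 = 9,198 / 4.1 = 2,243 dollars per point.

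**Unequal numbers contributing costs.** The literal numerator is n_L × (c + 146) − n_M × c.

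- 63 lifestyle, 70 MNT: 9,198 − 7c, which is zero at c = 9,198 / 7 = 1,314 dollars.
- 70 lifestyle, 63 MNT: 10,220 + 7c.

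Dividing by 4.1:

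| Assumed MNT cost c (dollars) | 63 lifestyle v 70 MNT (dollars per point) | 70 lifestyle v 63 MNT (dollars per point) | Per participant (dollars per point) |
|---|---|---|---|
| 432 | 1,506 | 3,230 | 35.6 |
| 1,000 | 536 | 4,200 | 35.6 |
| 1,314 | 0 | 4,736 | 35.6 |
| 2,000 | −1,171 | 5,907 | 35.6 |
| 5,000 | −6,293 | 11,029 | 35.6 |

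The lowest value, 432 = 578 − 146, is only an anchor. The 578 is program cost and the 146 also nets in medication changes, so 432 does not estimate MNT cost. A 63 against 70 split is what 10% drop-out would give if it fell wholly on one arm and those participants supplied no costs.

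**The case against.** The strongest reply is that total means all cost components added together for one participant. Section V lists several components per arm and elsewhere uses total for adding up time and its cost. The formula is introduced as the cost of each treatment model, and the same team reported its pilot per patient. The sentence on totals in each arm stands under cost of services and is not expressly tied to the formula. This reading is plausible. A reader might infer that the analysis will be done wrongly, and the documents do not show that. But no methods text states the per-participant reading, and the one sentence that gives a level gives the arm.

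Other inferences also go too far:

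- **That the 70-fold gap is in itself a wrong answer.** With equal arms it is a common multiplier that leaves sign and ranking intact, and 1:1:1 allocation within site limits imbalance at randomization.
- **That the ratio scales with drop-out.** Proportionality holds for the number contributing costs. Service costs come partly from billing data, and personnel costs from sessions delivered and visit notes, so a missed research visit need not remove a person's costs.
- **That a payment per patient is the stated purpose.** Sections II and V speak only of the design of payment contracts, and Aim 3 does not say per participant.
- **That costs are raw with respect to baseline.** Section V counts savings from lower medication use, and the pilot used changes in medication cost, so baseline use may already enter. The formula does not show how.

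The planned Monte Carlo work addresses uncertainty. It does not repair a mismatch of units.

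**Conclusion.** The point holds as a defect in a stated definition. Followed literally, the formula gives about n times the per-participant ratio (2,493 against 35.6 dollars per point at n = 70). When unequal numbers contribute costs, it can reverse sign while the cost difference per person is unchanged. The unit mismatch rests on the text alone.

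The size and the reversal are illustrations. They use pilot values from a 19-week program, whereas this trial's intervention runs to 24 months. Section I gives no horizon for the 146 dollars, and the 4.1 points are a 6-month effect. The reversal further assumes a 63 against 70 split in those contributing costs and an MNT cost above 1,314 dollars per participant, a figure the documents neither give nor exclude. The correction is cheap and should be made before the cost analysis.

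**What to change.** In Section VI.d (Aim 3) and in the matching sentence of Section V, replace total cost with mean total cost (all components) per randomized participant. State one horizon for costs. Say how incomplete cost follow-up will be handled, for example by multiple imputation or inverse-probability weighting. Compute mean percent weight loss on the same participants over the same horizon. Shared costs such as training and session delivery can be divided by the number randomized to the arm, with the rule stated.

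As a secondary improvement, adjust the comparison of medication and service-use costs for the RV1 medication and utilization data, and for center and sex, the randomization strata. Program and personnel costs have no baseline value, so the adjustment does not apply to them. Any gain in precision depends on a baseline to follow-up correlation that the documents do not give.

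The cost is a few edited sentences, one rule for incomplete costs and, if the adjustment is adopted, one regression. All of it uses data already planned for collection.

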A Data Safety Monitoring Plan will be implemented. The PI will review the safety and progress of this study on a monthly basis. In addition, the PI will include results of the review in the annual progress reports submitted to the IRB. The annual report will include a list of adverse events. It will address: 1) whether adverse event rates are consistent with pre-study assumptions; 2) reason for dropouts from the study; 3) whether all participants met entry criteria; 4) whether continuation of the study is justified on the basis that additional data are needed to accomplish the stated aims of the study; and 5) conditions whereby the study might be terminated prematurely.

b. Safety monitoring

The study will employ a Data Safety Monitoring Board of three independent clinical investigators (a primary care physician, an endocrinologist, and a psychologist) not affiliated in any way with the REAL HEALH-Diabetes study. The DSMB will be charged with overseeing rates of recruitment, eligibility criteria, protocol adherence, and the tracking of patient safety. The DSMB will establish its own independent meeting schedule and will determine what, if any, safety stopping rules will be necessary. At a minimum, the DSMB will meet with the PI (s) and co-investigators bi-annually the first year and then annually to evaluate the progress of the study and any safety concerns.

The major safety issues in this low-risk study will be the potential for participants to experience hypoglycemia and/or hypotension as weight loss occurs in those taking sulfonyureas and/or insulin and blood pressure medication. Based on our pilot trial (in which no severe hypoglycemia

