was reported) and 11+ years experience in the Look AHEAD study during which cases of self-reported/self-treated hypoglycemia were rare, and no episodes of severe hypoglycemia were reported in the lifestyle intervention group at our center, we do not anticipate any substantive hypoglycemia issues in the proposed study. Severe hypoglycemia is defined as any episode of loss of consciousness/ seizure or documented hypoglycemia (glucose < 70 mg/dl or 3.9 mmol/l) that prevents self treatment, or requires hospitalization or treatment by emergency personnel. Minor hypoglycemia is defined as self-reported transient symptoms such as lightheadedness, tremor, shaking, sweating, tingling, blurry vision, trouble concentrating etc., in combination with a documented low blood sugar value that are self-treated by ingestion of carbohydrates and resolved on their own or within 15 minutes of such self-treatment.

As a precaution, we will require the participants to self-monitor blood glucose and report any incidences of hypoglycemia. In such cases, the study providers will review the records and incidences of hypoglycemia and decrease/adjust medications as needed. In addition, the study provider will review glucose logs of all participants taking medications that cause hypoglycemia (insulin and sulfonylurea) weekly during the first 14 weeks of the study and then bi-weekly in weeks 15-26 so that they may pro-actively reduce those medications as participants lose weight and blood sugars hit 80-100 mg/dl, the low end of the ADA target range of 80-130 mg/dl. The hypoglycemic management guidelines are attached and based on the Look AHEAD trial algorithm. [See “10. Look AHEAD algorithm for medication adjustment based on blood glucose results”]

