Since the need for blood pressure medications decreased in both Look AHEAD and our pilot study in the active lifestyle intervention group, we will monitor blood pressure at baseline and at data collection visits as well as evaluate any symptomatic orthostasis reported by participants during the course of the study. For patients on blood pressure medication, it is recommended that for every 10 lbs of weight loss, participants obtain a seated blood pressure measurement either at a pharmacy and/or a visit to the health center. If a seated blood pressure is less than 100/70, or participant complains of lightheadedness with blood pressure less than 110/70, either at a research outcome visit or by self-report, one blood pressure medication will be held under the supervision of the study provider with notification of the referring provider and instructions to follow up with the referring provider for blood pressure measurement.

All participants will be given a handout on recognition of management of hypoglycemia and the protocol for blood pressure monitoring in their study materials [See “21. Handouts”].

Study staff will report all adverse events to the PI who will document and log them. The Log will include the PI’s evaluation of each event based on severity, whether it is related/unrelated to the study intervention, and if the event is anticipated/unanticipated. Based on that determination, the PI will follow the reporting requirements to the IRB within the required time frame. The Adverse Events Log will be provided to the DSMB on a quarterly basis.

Study staff will have each completed an IRB-required course in ethics and confidentiality in clinical research. Data will be gathered in a subject file that will be identified by number only, kept in a locked cabinet, and be made available only to authorized, trained study staff.

c. Adverse event reporting guidelines

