Each subject is evaluated for any adverse events. Any event that is reported to either the PIs, co-investigators, or the study staff by the subject or medical staff caring for the subject and which meets the criteria will be documented as such. Any event that is reported will then generate an adverse event report, which will be submitted to the IRB. The report will include a description of the event, when and how it was reported, as well as any official chart records or documentation to corroborate the event or the reporting of the event. Any severe and/or unanticipated adverse event will be immediately reported to the IRB. All other adverse events will be reported in a timely fashion to the IRB preferably within 2 weeks of the date of the event. All adverse events will be summarized annually and submitted to the IRB.

d. Data integrity

The research team will ensure that the documentation of all consent forms, questionnaires and diaries are adequate and accurate. Electronic data capture will be stored on RedCAP, the Partners Research Computing HIPAA and research-compliant electronic data capture system. The research team will also ensure that all paperwork is securely stored in locked drawers.

Documents that include participants' PHI will be kept separately from documents that include the participants' study code.

The research team will maintain confidentiality of data. All study demographic and survey data will be entered by study staff to RedCap. Each participant will be given a coded ID. A master key of the coded IDs and participant MRNs will be kept in a secure and password protected file by the PI as well as within RedCap. Only study staff that requires access to the password protected file or RedCap will be given access to it.

Separation of subject names and identifiable health information from the data will be done through the use of unique identifiers. All information transferred via the Internet will be done using at least 128-bit SSL encryption. All email sent out of the Partners firewall will be sent through Send Secure if any medication or diagnoses are included. Virus and password-protected facilities will be provided for the research team. All mobile devices will be encrypted to the standard defined by the Partners Laptop and Portable device encryption policies.

X. REFERENCES

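### Milder hypoglycemia and low-blood-pressure symptoms between visits are logged only when reported, and the lifestyle arms have far more scheduled occasions to report them than the MNT arm

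*Combined protocol and SAP*

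**What the plan says.** Section IX.b names the harms of interest: "The major safety issues in this low-risk study will be the potential for participants to experience hypoglycemia and/or hypotension as weight loss occurs". For hypoglycemia it says "we will require the participants to self-monitor blood glucose and report any incidences of hypoglycemia". Minor hypoglycemia is defined as self-treated symptoms "in combination with a documented low blood sugar value". For blood pressure, staff take readings at baseline and at data collection visits, and will "evaluate any symptomatic orthostasis reported by participants during the course of the study". For participants on blood pressure medication, a seated reading under 100/70, or under 110/70 with lightheadedness, leads to one drug being held, whether found at a research visit or self-reported.

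Section IX.c opens by saying that every subject is evaluated for adverse events. It gives no schedule, form or question set. What it does specify is the route into the record: "Any event that is reported to either the PIs, co-investigators, or the study staff by the subject or medical staff caring for the subject". Section IX.b adds "The Adverse Events Log will be provided to the DSMB on a quarterly basis".

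The contact schedule differs by arm. Section IV.c gives the lifestyle arms 14 weekly and then 5 biweekly sessions in six months, monthly sessions from month 6 to 24, and up to 5 individual dietitian visits. It places twice-daily glucose testing and weekly submission of records, for those on drugs that can cause hypoglycemia, within that program. Section VII agrees: "Participants in the group lifestyle intervention will be asked to submit weekly food, activity and blood glucose records". It leaves usual-care participants with their own primary care physician. The MNT arm's dietitian visits are billed usual care (IV.c). All arms have research visits at 6, 12, 24 and 36 months (V).

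**The concern.** Events that are logged on report are counted more fully where there are more occasions to report. The arms differ in those occasions by design. They also differ in how often a low glucose value would be on record, which the definition of minor hypoglycemia requires.

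If the milder events were equally common in all arms, the log would tend to show more of them under the lifestyle program. If they were truly more common there, the excess would tend to look larger than it is. The program is meant for wider use, so its apparent safety against standard care matters. An unprompted minor event in the MNT arm that nobody recorded cannot be recovered at analysis.

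**Working it through.** **1. Scheduled study contacts after baseline**

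Inputs: session schedule from IV.c, research visits from V, six-monthly calls from the Aim 3 cost section and Table 2.

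- Lifestyle sessions to month 6: 14 + 5 = 19, which matches the plan's own figure.
- Lifestyle contacts to month 6: 19 + 1 research visit = 20. MNT: 1 research visit.
- With the six-monthly call counted as a separate contact: 21 against 2.
- To month 24: 19 + 18 monthly sessions = 37; adding 3 visits and the 18-month call gives 41. MNT: 3 + 1 = 4.
- The optional individual visits (up to 5) are left out, as is the MNT arm's usual-care dietitian visit.

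**2. Is there a common question that would level this?**

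Table 2 lists 25 forms. None is titled for adverse events, hypoglycemia or low-pressure symptoms, and the content lists for the research visits and the 18-month call contain no such item. The forms themselves are not reproduced, so this rests on titles and listed domains.

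**3. Which harms are affected?**

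| Harm | Capture common to all arms | Capture that depends on contact |
|---|---|---|
| Measured low blood pressure | Duplicate readings at research visits (V, IX.b) | Self-reported readings between visits |
| Severe hypoglycemia | Emergency visits and admissions by calendar and six-monthly call (V, Aim 3) | Severe events that led to neither |
| Minor hypoglycemia | None named | Report, plus a documented low value |
| Lightheadedness between visits | None named | Report |

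**4. How far could unequal contact matter?**

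This is an illustration, not an estimate. Assume events spread evenly over 26 weeks, full session attendance, and reporting only at a scheduled contact within w weeks of the event. Lifestyle contacts fall at weeks 1 to 14, 16, 18, 20, 22, 24 and 26; the MNT contact falls at week 26. For w of 2 weeks or more, every lifestyle week is covered, so lifestyle coverage is 26/26. MNT coverage is w/26.

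| Recall w (weeks, assumed) | Lifestyle | MNT | Ratio |
|---|---|---|---|
| 2 | 100% | 7.7% | 13 |
| 4 | 100% | 15.4% | 6.5 |
| 8 | 100% | 30.8% | 3.25 |
| 13 | 100% | 50% | 2 |
| 26 | 100% | 100% | 1 |

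Clinician reports and unscheduled reports would pull these ratios toward 1, and so would missed sessions. The documents give no value for w or for any of these.

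**5. Would a test be misled?**

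Assume equal true risk, 90% of lifestyle events captured, and 70%, 50% or 30% of MNT events captured. The apparent risk ratio is 0.9/0.7 = 1.3, 0.9/0.5 = 1.8 or 0.9/0.3 = 3.0. The chance of a two-sided Fisher p below 0.05, for 140 lifestyle against 70 MNT participants, is:

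| True risk (assumed) | Equal capture | MNT 70% | MNT 50% | MNT 30% |
|---|---|---|---|---|
| 2% | 2.1% | 1.1% | 0.4% | 0.2% |
| 5% | 3.1% | 2.7% | 3.7% | 6.7% |
| 10% | 3.5% | 4.9% | 11.9% | 29.2% |
| 20% | 4.0% | 9.0% | 29.5% | 67.4% |

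A false signal is likely only at event risks well above what IX.b leads one to expect, since it describes self-treated hypoglycemia as rare in earlier experience. These figures do not carry the point. The apparent ratio is distorted at any risk.

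**The case against.** The strongest reply has four parts.

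*The plan says log review covers everyone at risk.* Section IX.b states that "the study provider will review glucose logs of all participants taking medications that cause hypoglycemia (insulin and sulfonylurea) weekly during the first 14 weeks". Read literally, this includes MNT participants on those drugs and would remove much of the asymmetry for hypoglycemia. Willingness to self-monitor glucose is also an entry criterion for all. Against that, IV.c ties the review to the session schedule, VII assigns record submission to the lifestyle arms, and no route for MNT participants to submit logs is described. Lifestyle only is the better reading, but the sentence is ambiguous and the objection stands to that extent.

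*Other routes exist.* Treating clinicians may report, and health-center clinicians serve as co-investigators. The handout on hypoglycemia and blood pressure monitoring goes to all participants. This narrows the gap by an unknown amount. Nothing described prompts an MNT participant's own physician to report.

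*Capture is already equal for part of the harm.* This is correct. A reader might infer from the contact counts that ascertainment of both named harms as a whole is unequal. The documents do not support that: research-visit blood pressure and health-service use are collected in every arm.

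*No by-arm adverse-event comparison is stated.* Also correct. VI.b lists no adverse-event outcome, IX.a compares rates with pre-study assumptions, and nothing says that the log goes to the DSMB by arm. A reader might infer that the trial is set up to declare a false safety difference. It is not. The point is conditional on someone reading the log by arm, which is foreseeable in a randomized trial but not planned.

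**Conclusion.** The concern holds in a limited form. For minor hypoglycemia and symptomatic low pressure between visits, the log depends on report, no common question is named, and scheduled contacts by month 6 are 20 against 1 (21 against 2 with a separate call). A by-arm reading of those entries would mix harm with opportunity to report. For measured hypotension and for severe hypoglycemia that leads to emergency care or admission, the problem is smaller.

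The contact counts come from the schedule and assume that it is followed. The view that log review is lifestyle only is an interpretation, though the better supported one. The size of the distortion is unknown: the coverage ratio runs from 13 down to 1 over the recall periods shown, and event risk and clinician reporting are not given. The weight endpoint and the stated efficacy analyses are not affected. This is worth considering as a low-cost improvement and is not a flaw in the main comparison.

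**What to change.** At the remaining 6, 12, 24 and 36 month visits and on the 18-month call, ask the same short questions in the same words in all three arms:

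- severe hypoglycemia since last asked;
- symptoms of hypoglycemia in the past 4 weeks, recorded with and without a documented low glucose;
- lightheadedness on standing in the past 4 weeks;
- any blood pressure drug held, and why.

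Base any by-arm safety summary on these answers, research-visit blood pressure, and emergency visits and admissions. Give counts with 95% intervals and no test. List events found through sessions or glucose logs separately, for safety management and not as an arm contrast. State in IX.b whether glucose-log review covers MNT participants. Where visits have already passed, report the log with contact counts by arm.

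The cost is about four questions at contacts that already take place, one table and one clarifying sentence. Limits remain. Mild events outside the recall period are missed in every arm. Lifestyle participants test more, so recognition and documentation of low glucose may still differ, which is why symptoms without a documented value should be recorded too. Visit readings may understate low pressure in the lifestyle arms if it is corrected between visits.
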